4.7.3 Anticoagulation Use

Rate of anticoagulation: The key indicator of the choice to start an anticoagulant will be its prescription in the EMR prescription module (observed discussions and patient/clinician accounts may not reflect decisions confirmed after the visit with a prescription, for example, after the clinician or the patient checked other information or with other informants). After this primary ‘decided as prescribed’ approach, we will conduct secondary analyses using patient/clinician reported and video-observed decisions. Decisions may be for starting or not an anticoagulant in the start cohort. It is possible that there may be some decisions to stop anticoagulation in the review cohort, but we expect start and review cohorts to contribute information about choice of anticoagulant.

Choice of anticoagulant: We will review the EMR and 10-month pharmacy profiles (to stand for the 12-month profile given the automatic expiration of pharmacy records at 1 year) to determine the prescribed anticoagulant and whether and when switches to another agent or to no anticoagulant took place.

Together, they should capture choice and switches even when these occur as a result of changes in clinician (e.g., from cardiology to primary care). When available, we will note the documented reasons from clinical notes for choosing and switching as well as with which clinician the change was made (e.g primary, cardiology, etc.).

Anticoagulation persistence: Patients will identify the pharmacy(-ies) they use to fill their prescriptions and authorize us to obtain their prescription drug fill data. We will calculate anticoagulation persistence, using the percent days covered (PDC) based on prescription refill behaviors (total days supply of anticoagulant filled / total days of observation from the first prescription fill date; range 0-100%). We will also pull all pharmacy refills for the 12 months prior to enrollment. This will allow us to calculate persistence for prior use of anticoagulants for the review cohort to compare to persistence post encounter and see if there is an impact.

Warfarin use: For patients who choose to stay on warfarin, we will also use as secondary measures of adherence: (a) the proportion of INR tests obtained/scheduled; and (b) percentage of time at therapeutic target (typically INR 2-3).

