4.9.2 Sample Size Estimation

*The table shows the detectable effect for each of the outcomes of interest if we were to have data on that outcome from a total of 333 patients (1% of available population). This provides enough power ($\alpha=0.05$; two-sided difference) to detect meaningful differences across arms for all SDM quality and process outcomes. Our intent, however, is to have enough power to detect important differences when we conduct analyses of groups or cohorts of patients. Most of these analyses will divide the participants into 2 cohorts (e.g., start and review cohorts), except for the subgroup analysis by clinic, which divides the total sample into 3 cohorts: academic, community, and safety net clinic. That is the only analysis with three groups. Given this, we would need 3 times the sample size listed in the table, or **999 participants (3% of available sample)** to address all planned subgroup analyses. These are minimum targets for recruitment and we do not plan to limit recruitment in any way to enroll up*

to this number of patients. It assumes even distribution of participants per subgroup (e.g., start vs. review cohort); since the only grouping with three levels is clinic, each clinic will be expected to recruit similar numbers. Thus, for the main analysis and for other subgroup analyses (n=2 levels),

Outcome (n = 333)	Rate (%) or SD	Detectable effect	Power*
Patient level – SDM quality			
Knowledge transfer [^]	18	5.6	84%
Knowledge of risk	55%	15%	81%
Decisional conflict scale [^]	17	5.2	80%
Clinician level			
Satisfaction [^]	54%	15%	80%
Encounter level – SDM process			
Engagement (OPTION12) [^]	12.6	3.9	80%

[^] Values from iADAPT SDM tool trial; * $\alpha=0.05$; two-sided

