We expect approximately 90% of patients to start (start cohort) or continue a medication (review cohort). Of those, we can reasonably expect to obtain >85% of the pharmaceutical records for those (records will be requested of all enrolled patients regardless of decision). Thus, using the trial size estimated of **999 participants**, we will have ~765 patient records available for assessment of anticoagulant persistence at 12 months (PDC). In our review of the Optum database, 40% of patients were adherent to anticoagulation (>80% PDC, the threshold used by CMS) at 12 months. Assuming an expected rate of 60% PDC for the usual care cohort, we would have 80% power to detect a 9% difference (69% PDC in the SDM tool arm), with a two-sided test and an alpha of 0.05. In subgroup analyses comprising 100 participants per arm and using a one-sided test and alpha of 0.05, we will have 80% power to detect differences of at least 16%.

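### Persistence power is overstated: read as proportions of patients with 1:1 allocation, about 765 records give about 74% power for 60% versus 69%, not 80%

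*Combined protocol and SAP*

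**What the plan says.** Section 4.9.2 (Sample Size Estimation) gives the persistence calculation after the main table. Starting from 999 participants, it expects about 90% to start or continue an anticoagulant and more than 85% of pharmacy records to be obtained for those patients. It concludes that "we will have ~765 patient records available for assessment of anticoagulant persistence at 12 months (PDC"). It then mentions a database review in which 40% of patients were adherent, defined as PDC above 80%, and continues: "Assuming an expected rate of 60% PDC for the usual care cohort, we would have 80% power to detect a 9% difference", with 69% in the tool arm, a two-sided test and alpha 0.05.

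For subgroups of 100 per arm, with a one-sided test at 0.05, the same section says "we will have 80% power to detect differences of at least 16" percentage points.

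Section 4.7.3 (Anticoagulation Use) defines PDC per patient as "total days supply of anticoagulant filled / total days of observation from the first prescription fill date; range 0-100" percent. No standard deviation for PDC appears anywhere. Section 4.9.3 (Patient Allocation) describes stratified randomisation in blocks of random size but gives no allocation ratio.

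**The concern.** The number of records, the two rates, the sidedness and the alpha are all printed, so the stated power can be recomputed once a reading of the rates and an allocation ratio are fixed. On the natural reading, it does not come out at 80%.

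This is the only place where the plan says what overall difference in persistence it can detect. Anyone interpreting a null persistence result will turn to this sentence. On the plan's own inputs, the chance of missing a true 9-point difference is about 26% rather than the 20% implied.

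**Working it through.** **Inputs (section 4.9.2 unless noted)**
- Records: 999 × 0.90 × 0.85 = 764.2, which reproduces the plan's ~765.
- Rates: p₁ = 0.60 and p₂ = 0.69, read as proportions of patients.
- Two-sided alpha 0.05, so z = 1.960.
- Allocation 1:1 (an assumption; section 4.9.3 gives no ratio), so n = 382.5 per arm.

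**Does the formula match the plan's other figures?**

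The formula is power = Φ[(|p₂ − p₁| − z·SE₀)/SE₁], with SE₀ = √(2p̄(1 − p̄)/n) and SE₁ = √((p₁(1 − p₁) + p₂(1 − p₂))/n).

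| Figure in section 4.9.2 | Stated | Recomputed |
|---|---|---|
| Knowledge of risk, 55% v 70%, n = 333 | 81% power | (0.15 − 1.960 × 0.05306)/0.05242 = 0.878, so 81.0% |
| Clinician satisfaction, 54% v 69%, n = 333 | 80% power | (0.15 − 1.960 × 0.05333)/0.05269 = 0.863, so 80.6% |
| Subgroup, 100 per arm, one-sided, 60% base (carried over; not stated for this sentence) | 16 points | 16.3 points at 80% power |

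**Overall persistence figure**
- p̄ = 0.645
- SE₀ = √(2 × 0.645 × 0.355/382.5) = 0.03460
- SE₁ = √((0.2400 + 0.2139)/382.5) = 0.03445
- (0.09 − 1.960 × 0.03460)/0.03445 = 0.644, and Φ(0.644) = **74.0%**, against 80% stated.

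Other two-sided methods agree: unpooled 74.3%, arcsine 74.1%, exact enumeration of the chi-square test 74.2%, continuity-corrected 71.5%. A one-sided test would give 83.2%, but the sentence specifies two-sided.

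**What 80% power would require**
- Per arm: (1.960 × √0.45795 + 0.842 × √0.4539)²/0.09² = 442.6, so 443 per arm or 886 records.
- With 765 records, solving the power formula for the difference gives 9.66 points (60% v about 69.7%).

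**Sensitivity to retrieval (999 enrolled, 90% users, exactly 9 points)**

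| Records retrieved | Records | Power |
|---|---|---|
| 85% | 764 | 74.0% |
| 90% | 809 | 76.4% |
| 95% | 854 | 78.6% |
| 100% | 899 | 80.6% |

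Power reaches 80% only at 886/899.1 = 98.5% retrieval. At 90% × 85%, enrolment would have to be 886/0.765 = 1,158.2, so 1,159.

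**Sensitivity to allocation.** Unequal arms lower power: 72.6% with the larger tool arm at 1.5:1, and 68.5% to 69.5% at 2:1, depending on which arm is larger.

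**The mean-PDC reading.** Power for a 9-point difference in means is Φ(9/(SD × √(2/382.5)) − 1.960). The plan gives no SD, so these values are assumptions: SD 30 gives 98.6%, 35 gives 94.5%, 40 gives 87.5%, 45 gives 79.0%. Exactly 80% needs an SD of about 44.4. The largest possible SD for a 0–100 quantity with mean 60 is √(60 × 40) = 49.0.

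**The case against.** The strongest objection is that the sentence may concern mean PDC. It attaches the percentages to PDC itself, and section 4.7.3 defines PDC as a continuous quantity for each patient. The preceding adherence figure is 40%, so the 60% is not simply that proportion carried forward. A single SD of about 45 would give detectable differences of about 9.1 points overall and 15.8 to 15.9 points in the subgroup, close to the stated 9 and 16. The subgroup sentence therefore does not separate the two readings. This part stands: the proportion reading is likelier, not certain. In its favour, the text speaks of a rate, directly after a proportion of adherent patients. The table in the same section gives an SD for its continuous outcomes, while this sentence gives none. An SD near 45 against a ceiling of 49 would mean nearly all-or-nothing PDC values. On the mean reading, the sentence is incomplete rather than shown to be wrong.

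Second, the inputs are floors. Retrieval is given as more than 85%, and on recruitment the plan says "These are minimum targets for recruitment and we do not plan to limit recruitment in any way". Records are also requested from all participants; 85% of 999 is 849 records and 78.3% power. But the paragraph bases its calculation on 999 participants and about 765 records, and even 95% retrieval among users leaves power at 78.6%.

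Third, rounding. Taking 69% as 69.49% gives 78.6% at 765 records, and about 80% only with about 791 records (88% retrieval). Truncating 9.66 to 9 could explain how the figure arose, but it would still understate the difference detectable at 80% power.

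**Conclusion.** The stated 80% does not follow from the plan's inputs. With about 765 records, power for 60% versus 69% is about 74%, and the difference detectable at 80% power is about 9.7 points rather than 9. This rests on two assumptions: that the percentages are proportions of patients, and that allocation is 1:1. The unequal ratios tried only widen the gap. If mean PDC was meant, the claim cannot be verified without an SD. The documents do not show how the 80% was obtained.

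The point is minor. Aim 2 is descriptive, and the 999 was set by the three-way clinic subgroup analysis, not by persistence. The detectable difference moves by about 0.7 of a point.

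**What to change.** In section 4.9.2, restate the sentence in one of two equivalent ways for about 765 records, two-sided alpha 0.05 and 1:1 allocation:
- about 74% power to detect 60% versus 69%; or
- 80% power to detect a difference of about 9.7 points from 60%.

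Say explicitly that 60% and 69% are the shares of patients with PDC above 80%, and state the allocation ratio. If mean PDC was intended, say so, give the SD and its source, and recompute both the overall and the subgroup figures.

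The cost is one sentence of protocol wording. Enrolment, endpoints and analyses do not change.

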4.9 Statistical Analysis

4.9.1 Analysis Plan

The study will be analyzed according to the *intention to treat principle (ITT)*, including all patients enrolled to the study in the arm to which they were assigned, regardless of which they were assigned to (e.g., standard care or Anticoagulation Choice + Standard Care). Reporting will include 'Per Protocol', complete data for each arm plus the ITT analysis where imputation analysis methods will be utilized to address any missing values (see section 4.9.1.1 for details on missing data analysis). Baseline characteristics will be reported in the study results with continuous values being reported as means and standard deviations and categorical values reported as counts and frequencies and compared between study arms using t-tests and chi-squared tests. Any baseline imbalances ($p < 0.05$) will be explored as a possible factor to adjust for when the outcome measures are

analyzed. We will adhere to the CONSORT guidelines to transparently report study results and ensure that sufficient information is included to allow for assessment of the study's internal and external validity.

We will use standard techniques appropriate for trials, with each outcome compared between study arms using t-tests for continuous outcomes and chi-square tests for dichotomous outcomes. If there are differences in baseline characteristics found by statistical means or found to have clinical relevance between the two study groups, these will be accounted for using regression models which include an indicator for study arm.

We will perform descriptive analyses to describe any potential heterogeneity of treatment effect (HTE) and facilitate synthesis of subgroup results in future meta-analyses. We will conduct descriptive HTE analyses by clinic (academic, community and safety net), by cohort (start or review cohort), by stroke risk (CHA₂DS₂-VASc score of 1 or ≥ 2 for men and 2 or ≥ 3 for women), and by numeracy (Less than adequate vs. not). The outcomes assessed with HTE analyses will be the same as those assessed in the trial (e.g., SDM and communication quality, knowledge, and decisional satisfaction).

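### Section 4.9.2 does not say whether persistence is mean PDC or the share of patients above 80% PDC, and its 80% power for a 9-point difference is not supported on either reading

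*Combined protocol and SAP*

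**What the plan says.** - Section 4.7.3 (Anticoagulation Use) defines persistence for each patient as "total days supply of anticoagulant filled / total days of observation from the first prescription fill date; range 0-100" percent. That is a continuous quantity, and the section sets no threshold.
- Section 4.9.2 (Sample Size Estimation) reports from the Optum database that "40% of patients were adherent to anticoagulation (>80% PDC, the threshold used by CMS) at 12 months". That is a yes/no measure. The section cites it as a benchmark and does not expressly make it the trial outcome.
- The next sentence gives the planning values: "Assuming an expected rate of 60% PDC for the usual care cohort", then "we would have 80% power to detect a 9% difference (69% PDC in the SDM tool arm"). The significance level for this comparison is 0.05, two-sided.
- The sample behind this is also given: "we will have ~765 patient records available for assessment of anticoagulant persistence at 12 months (PDC").
- Section 4.9.1 (Analysis Plan) chooses the test by outcome type: "t-tests for continuous outcomes and chi-square tests for dichotomous outcomes".
- The detectable-effect table in 4.9.2 gives each listed outcome either a rate or an SD. Persistence is not in that table, and no SD for PDC appears anywhere.

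**The concern.** The planning sentence can be read in two ways. A figure of 60% PDC sounds like a mean of the 4.7.3 quantity. The word rate, the missing SD and the preceding sentence about patients above 80% suggest a proportion. The two readings need different tests and different inputs to the power calculation. Because no section settles the choice, the form of the outcome could be decided after the data are seen.

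The power sentence is the only statement of what the trial can show on persistence. Section 4.9.2 powers it as a two-sided comparison between arms, so a reader will expect a test. If the sentence does not hold on either reading, that reader cannot tell what size of difference a null result would make unlikely.

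**Working it through.** **Inputs.** From 4.9.2: 999 participants, 90% starting or continuing a drug, 85% of records obtained, 60% v 69%, two-sided alpha 0.05, stated power 80%. For subgroups: 100 per arm, one-sided 0.05, 80% power for 16 points. Assumptions: 1:1 allocation (no ratio is stated) and, for the mean reading only, a range of SDs.

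**Records.** 999 × 0.90 × 0.85 = 764, which matches the stated 765 or so. Half of 765 is 382.5 per arm.

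**Reading 1: proportions.** With p̄ the average of the two rates,

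power = Φ{ [(p2 − p1) − 1.96 × √(2p̄(1 − p̄)/n)] / √(p1(1 − p1)/n + p2(1 − p2)/n) }.

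*The plan's own figure, 60% v 69%, n = 382.5.* Here p̄ = 0.645, the null standard error is 0.0346 and the alternative standard error is 0.0344. Power = Φ[(0.09 − 1.96 × 0.0346)/0.0344] = Φ(0.64) = **74%**. Other versions of the calculation do not recover 80%: unpooled variance 74.2%, arcsine 74.0%, continuity-corrected 71.4%, one-sided 83.2%. Solving the formula for 80% power gives a detectable difference of **about 9.7 points**, or 443 per arm (886 records) for 9 points. Using 999 × 0.90 = 899 records, without the 85% retrieval step, gives 80.6%. That is one possible origin of the stated figure, but the documents do not confirm it.

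*From the Optum rate, 40% v 49%, n = 382.5.* Here p̄ = 0.445 and the standard errors are 0.0359 and 0.0358. Power = Φ[(0.09 − 1.96 × 0.0359)/0.0358] = Φ(0.55) = **71%**. The difference detectable with 80% power is **about 10.1 points**.

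**Reading 2: mean PDC.** Detectable difference at 80% power = SD × √(2/n) × (1.96 + 0.84) = SD × √(2/382.5) × 2.80 = 0.2026 × SD.

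| Assumed SD | Detectable difference (points) |
|---|---|
| 25 | 5.1 |
| 30 | 6.1 |
| 35 | 7.1 |
| 40 | 8.1 |

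For the detectable difference to be exactly 9 points, the SD must be 9/0.2026 = **about 44**. The largest SD possible on a 0 to 100 scale with mean 60 is 100 × √(0.6 × 0.4) = 49, so 44 would mean that most patients sit near 0 or near 100.

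**Which reading was probably intended.** The subgroup statement helps. As two proportions starting at 60%, 60% v 76% with 100 per arm and a one-sided 0.05 test has 78.6% power, and 80% power needs 16.3 points. That nearly reproduces the stated 16. Starting at 40%, the same 16 points has 73.5% power. As means, 16 points would need an SD of 16/[(1.645 + 0.842) × √(2/100)] = about 45. Together with the word rate and the absence of an SD, this points to a two-proportion calculation starting at 60%.

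**The case against.** The strongest reply is that the intent is clear enough: the sentence follows one about patients above 80% PDC, it uses the word rate, and the subgroup figure nearly reproduces as two proportions. Most of this stands, and it is why the proportion reading is treated as the likelier one. It does not close the point. Section 4.7.3 still defines only the continuous quantity, and on the proportion reading the stated 80% comes out at 74%.

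A second reply is that little depends on the sentence. SDM quality is the primary endpoint, Aim 2 is worded as descriptive, and 999 was set by the SDM outcomes and the clinic subgroups. Persistence power was worked out afterwards from that number. This also stands and limits the importance of the point.

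A reader might go further in four ways that the documents do not support:

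- *That the 60% contradicts the 40%.* The 40% comes from an external database. The planning value is for trial participants who start or continue a drug and whose records are obtained. The gap is unexplained, but it is not a contradiction.
- *That power for the same effect swings widely with the definition.* With an assumed SD of 35, a 9-point shift in mean PDC has about 94% power, and setting that beside the 71% for 40% v 49% looks striking. These are different treatment effects. In an illustrative beta model with SD 35 in both arms, moving the mean from 60% to 69% moves the share above 80% from 41% to 55%, which has about 97% power. No power loss from the 80% cut-off is shown.
- *That 60% and 69% should be labelled as mean PDC.* The internal evidence points the other way.
- *That persistence is the leading Aim 2 endpoint.* Aim 2 covers rate, choice and adherence and ranks none of them first.

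**Conclusion.** The point holds in a limited form. The form of the persistence outcome, and so its test, is not fixed, and the statement of 80% power for 9 points is unsupported as written. On the proportion reading the shortfall is about 6 percentage points of power (74% against 80%), or a detectable difference of 9.7 rather than 9 points. Starting from the Optum rate, it is about 9 percentage points of power (71%) and 10.1 points. On the mean reading the figure cannot be checked without an SD. It would be right only at about 44; at assumed SDs of 25 to 40 the trial could detect smaller differences than it claims (5.1 to 8.1 points).

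These results assume 1:1 allocation, about 765 usable records and independent patients. The SDs are illustrative and come from no document. The primary comparison of SDM quality and the recruitment target do not depend on this sentence. It should be corrected because it is wrong as written and cheap to repair.

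**What to change.** 1. In 4.7.3 and 4.9.2, state which form of PDC is the lead persistence measure (mean PDC, or the share of patients above 80%) and which test from 4.9.1 applies. Name the other form as secondary. The choice belongs to the trial team and should be recorded before outcome data are examined.
2. Correct the power sentence in 4.9.2 to match that choice:
   - If the lead is the share above 80%, state about 74% power for 60% v 69%, or a detectable difference of about 9.7 points at 80% power. Then justify the 60% in view of the 40% Optum rate, or replace it; starting from 40%, the detectable difference is about 10.1 points.
   - If the lead is mean PDC, state the SD, its source, and the detectable difference that follows.
3. State the allocation ratio used in the calculation.

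The cost is wording in two sections, with no further patients, visits or trial data. The downside on the proportion reading is that the stated power for persistence becomes slightly less favourable.

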2.0 Background and Significance

Atrial fibrillation is the most common cardiac arrhythmia affecting ~3 million Americans^{1,2} It accounts for ~\$26 billion/year in healthcare costs.³ AF-related thromboembolic strokes are often devastating and a cause of great physical, social and economic burden.⁴⁻⁷ Vitamin K

antagonists (VKAs, e.g., warfarin) reduce the risk of stroke by ~68%.⁸⁻¹³ Recently, non-VKAs oral anticoagulants (NOACs) that directly inhibit factor Xa (e.g., rivaroxaban, apixaban, edoxaban) or thrombin (dabigatran) have demonstrated similar to or better efficacy and safety than warfarin.¹⁴⁻¹⁶ Underuse of anticoagulation is a significant quality gap. Despite patients' strong aversion to strokes,^{17,18} <50% of high-risk patients with AF receive anticoagulants.¹⁹ Of these, 30-50% stop treatment within 12 months.²⁰⁻²³ The low rate of anticoagulation suggests that clinicians are challenged in initiating anticoagulation, in part due to clinicians' aversion to causing anticoagulation-related bleeding,^{19,24} Nonadherence suggests that some patients cannot implement anticoagulation in their lives: warfarin requires a stable diet and periodic laboratory (INR) monitoring,²⁵⁻²⁷ while NOACs are costly and lack bleeding reversal agents.¹⁴⁻¹⁶ Underuse may result also from poor patient and clinician access to, and deliberation with, individualized estimates of risks and benefits.^{28,29} Patients and clinicians require support in initiating and implementing anticoagulation therapy.

In 2014, three major cardiovascular organizations formulated guidelines for the management of patients with AF. They gave their strongest class I recommendation for using SDM to individualize anticoagulation in at-risk AF patients.³⁰ SDM has the potential to support patients and clinicians in collaborative deliberation about reasonable anticoagulation strategies matched to medical risk and patient circumstance.³⁰⁻³² Nevertheless, this recommendation is based on expert consensus (level C evidence) and translating it into practice is challenging. The guideline provides no guidance on how to achieve this, and no tools were available that are both up-to-date and proven to support SDM in this context. Furthermore, we do not know what effect SDM may have on anticoagulation rates and adherence in patients with AF.³⁰

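### Persistence power in 4.9.2 rests on an unsourced 60% on an undefined scale; the main 80% is about 74% at that rate and 71% at the reported 40%, and the subgroup 80% falls to about 73.5% at 40%

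*Combined protocol and SAP*

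**What the plan says.** All the persistence sizing is in one paragraph of section 4.9.2. Starting from 999 participants, it expects about 90% to start or continue a drug and says "we can reasonably expect to obtain >85% of the pharmaceutical records for those", which leaves about 765 records. It then cites a review of the Optum database, in which "40% of patients were adherent to anticoagulation (>80% PDC, the threshold used by CMS) at 12 months". The next sentence reads "Assuming an expected rate of 60% PDC for the usual care cohort, we would have 80% power to detect a 9% difference", with 69% in the tool arm, a two-sided test and alpha 0.05. For subgroups of 100 per arm, with a one-sided test at 0.05, it adds: "we will have 80% power to detect differences of at least 16" percent.

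Two other places bear on the 60%. Section 4.7.3 defines PDC as days supplied over days observed, on a scale of 0 to 100%, and sets no cut-off. Section 2.0 says of patients who receive anticoagulants: "Of these, 30-50% stop treatment within 12 months".

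**The concern.** Two adjacent sentences give 40% and then 60%, with nothing to connect them. The 40% is the only figure in the documents for PDC above 80% at 12 months. The nearest support for 60% is the background statement on stopping, which implies that 50% to 70% continue. Continuing treatment is a different measure from having more than 80% of days covered.

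The label adds to the doubt. A rate of 60% PDC could mean 60% of patients above the 80% threshold or an average PDC of 60%, and the outcome definition does not settle it.

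At stake is whether the stated power and detectable differences for persistence, overall and in subgroups, can be relied on. Persistence is part of Aim 2, so these figures tell the reader how much the trial can say about it.

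**Working it through.** **Inputs from the plan.** 999 participants, 90% starting or continuing, 85% of records obtained: 999 × 0.90 × 0.85 = 764, stated as about 765. Main comparison: 9 points, two-sided 0.05. Subgroups: 100 per arm, 16 points, one-sided 0.05.

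**Assumptions.** Percentages are proportions of patients. Allocation is 1:1 (the ratio is not stated), so 765 / 2 = 382.5 per arm. There is no allowance for clustering by clinician, and the plan's own persistence statement mentions none.

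**Formula** (two-proportion z test, pooled variance under the null), with p̄ the mean of the two rates:

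power = Φ{ [ d − z·√(2p̄(1−p̄)/n) ] / √[(p1(1−p1) + p2(1−p2))/n] }

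**Main comparison, the plan's own rates (60% v 69%).**
- Null SE: √(2 × 0.645 × 0.355 / 382.5) = 0.0346
- Alternative SE: √((0.2400 + 0.2139) / 382.5) = 0.0344
- (0.09 − 1.96 × 0.0346) / 0.0344 = 0.644, so power is **74.0%**

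The stated 80% is not reproduced. Other versions of the test give 74.2% (unpooled), 74.0% (arcsine) and 71.4% (continuity-corrected); a one-sided test would give 83.1%. At these rates, 80% power needs 443 per arm (886 records).

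**Main comparison at 40% v 49%.**
- Null SE: √(2 × 0.445 × 0.555 / 382.5) = 0.0359
- Alternative SE: √((0.2400 + 0.2499) / 382.5) = 0.0358
- (0.09 − 1.96 × 0.0359) / 0.0358 = 0.547, so power is **70.8%**

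The gap to 80% is about 9 points: about 6 (80 − 74.0) exist at the plan's own rates, and about 3 (74.0 − 70.8) come from the lower control rate. The control-arm variance is the same at both rates (0.4 × 0.6 = 0.24), so the loss comes from the tool arm: 0.2499 at 49% against 0.2139 at 69%.

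**Subgroups, 60% v 76%.**
- Null SE: √(2 × 0.68 × 0.32 / 100) = 0.0660
- Alternative SE: √((0.2400 + 0.1824) / 100) = 0.0650
- (0.16 − 1.645 × 0.0660) / 0.0650 = 0.792, so power is **78.6%**, which agrees with the plan to rounding

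**Subgroups, 40% v 56%.**
- Null SE: √(2 × 0.48 × 0.52 / 100) = 0.0707
- Alternative SE: √((0.2400 + 0.2464) / 100) = 0.0697
- (0.16 − 1.645 × 0.0707) / 0.0697 = 0.628, so power is **73.5%**

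**Difference detectable with 80% power** (same formula solved for d):

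| Control rate | Main: power for 9 points | Main: 80% difference | Subgroup: power for 16 points | Subgroup: 80% difference |
|---|---|---|---|---|
| 60% | 74.0% | 9.7 points | 78.6% | 16.3 points |
| 40% | 70.8% | 10.1 points | 73.5% | 17.5 points |

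A control rate of 50% gives 70.5% (main) and 74.4% (subgroup), so a rate between the two figures would not rescue either statement.

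**If 60% is a mean PDC.** A 9-point difference in means with 382 per arm gives 80.7% power at an SD of 44 points and 98.6% at an SD of 30. The stated 80% therefore needs an SD of about 44 points, and the documents give none. The subgroup figure fits a proportion of 60%, which makes proportions the likelier reading.

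**The case against.** The strongest reply is that 40% need not be the right control rate. It describes patients in a database whose make-up and denominator are not given. The rate that the plan assigns to usual care is 60%. The trial's records come from patients expected to start or continue a drug, with PDC counted from the first fill, so participants could do better than the database. If 60% is a mean PDC, it can coexist with 40% of patients above the threshold, and the two figures need not conflict. This stands to the extent that the documents do not show 60% to be wrong. It does not remove the need to give the source and scale of the 60%, and it leaves the main figure at 74%.

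The stakes are also limited. Aim 2 is worded as descriptive, the primary endpoint is SDM quality, and 999 was reached by tripling the 333 used for the SDM outcomes. Persistence did not set the sample size. That argues for a modest correction and no redesign.

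A reader might go further and infer that a null persistence result would mislead because of the control rate. The documents do not say how such a result would be interpreted. With equal observed rates in the two arms, the 95% interval has the same half-width at 40% and 60%: 1.96 × √(2 × 0.24 / 382.5) = 6.9 points. Nor can the expected benefit be called misdescribed in relative terms, since the plan states only an absolute difference.

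**Conclusion.** The point holds in a limited form. The plan moves from a reported 40% to an assumed 60% without a reason and without defining the scale. Neither stated 80% power holds at 40%: the main figure is about 71% and the subgroup figure about 73.5%.

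It is tempting to conclude that the choice of 60% is why the main 80% fails. It is not the main reason: power is already about 74% at 60% v 69%, and moving to 40% shifts the detectable difference only from about 9.7 to 10.1 points. Justifying the 60% would therefore not restore the stated figure. About 899 records (999 × 0.90, without the 85% step) would give 80.6%, but the documents do not say that this is how the figure arose. Only the subgroup shortfall, from about 79% to 73.5%, is due to the control rate.

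These results rest on reading the percentages as proportions, 1:1 allocation, no clustering, and the plan's own record count, alpha and sidedness.

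**What to change.** In section 4.9.2:

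1. Define the persistence endpoint used for sizing, for example the proportion of patients with PDC above 80%, and align it with section 4.7.3.
2. Give the source of the 60%. If it means patients still on treatment, or a mean PDC, label it so; for a mean, give the SD.
3. Show both rates side by side. Main comparison, about 765 records, two-sided 0.05: at 60%, 74% power for 9 points and 80% for about 9.7 points; at 40%, 71% and about 10.1 points. Subgroups, 100 per arm, one-sided 0.05 as the plan has it: 80% power for about 16.3 points at 60% and about 17.5 points at 40%.

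This takes a few sentences or a small table. No extra patients or data are needed and recruitment does not change. The only cost is slightly less favourable stated power.
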